### Study Population

Patients diagnosed with severe acute kidney injury (AKI) who have been discharged from the hospital and receive nephrology follow-up at the Hospital Civil de Guadalajara “Fray Antonio Alcalde”, Guadalajara, Mexico. This group will include patients with diverse demographic and clinical characteristics who meet the inclusion criteria established in the study protocol.

### Observation Unit

Patients diagnosed with severe AKI will be monitored for a period of 90 days after hospital discharge. Each participant will be evaluated based on infection incidence, rehospitalization, adverse events, and other health outcomes related to trimethoprim–sulfamethoxazole administration. Observation will focus on collecting clinical data and health outcomes specific to each participant.

### Sample Size

To determine, with a 95% confidence level and 90% statistical power, whether the proportion of 59% in sample A differs from 29.5% in sample B, a total of 60 individuals per group will be required.

This study aims to detect a clinically significant difference of 0.8 ( $Z\alpha/2 = 1.96$ ,  $Z\beta = 0.84$ ) with a standard deviation of 1.5. Sample size calculations are based on the assumption

that approximately 30% of patients with AKI will experience a subsequent infection.

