### Materials and Methods

- This study will be a phase 2, randomized, prospective, double-blind, investigator-initiated, parallel-group, placebo-controlled clinical trial conducted at the Hospital Civil de Guadalajara “Fray Antonio Alcalde”, Guadalajara, Mexico. All patients with AKI receiving nephrology consultation will be considered for inclusion.
- The diagnosis of AKI will follow the Kidney Disease: Improving Global Outcomes (KDIGO) serum creatinine criteria. In accordance with the recommendations of the 31st Acute Disease Quality Initiative Group regarding the design of clinical trials for AKI treatments, the subphenotype of patients at the highest risk of post-AKI infections will be selected. This study will be considered a phase 2 randomized, double-blind, placebo-controlled trial meeting efficacy (AKI trajectory and eGFR evaluation), feasibility (patient recruitment and protocol adherence), and safety (adverse events and drug reactions) objectives.
- Group randomization will be performed using the clinical trial randomization tool available at <http://www.winepi.net/f108.php>, employing traditional block randomization. Sequences for each arm and stratum will be generated using maximal asymptotic randomization.
- Patients will be recruited on an outpatient basis to document any infectious event of any kind occurring within the first 90 days, as well as cases of rehospitalization due to infection within the same period at the Hospital Civil de Guadalajara “Fray Antonio Alcalde”.

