## Operationalization of Variables

### Independent Variable:

- Treatment: Administration of the study drug versus placebo (categorical variable with two levels: active treatment or placebo).

Dependent Variables (Primary Outcomes):

- Development of gastrointestinal infections — categorical nominal binary variable (yes/no)
- Development of upper respiratory infections — categorical nominal binary variable (yes/no)
- Development of lower respiratory infections — categorical nominal binary variable (yes/no)
- Development of urinary tract infections — categorical nominal binary variable (yes/no)
- Development of soft tissue infections — categorical nominal binary variable (yes/no)
- Rehospitalization due to infection — categorical nominal binary variable (yes/no)
- Development of septic shock — categorical nominal binary variable (yes/no)
- Requirement for long-term renal replacement therapy — categorical nominal binary variable (yes/no)
- Death from any cause — categorical nominal binary variable (yes/no)
- Progression to chronic kidney disease or  $\geq 50\%$  decline in eGFR — categorical nominal binary variable (yes/no)
- Worsening renal function with  $\geq 25\%$  decline in eGFR due to infection — categorical nominal binary variable (yes/no)
- Presence of hyperkalemia — categorical nominal binary variable (yes/no)
- Adverse drug reactions — categorical nominal variable

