#### Statistical Analysis

An intention-to-treat approach will be adopted, including all randomized participants who receive the intervention, for both primary and secondary outcomes.

Categorical variables will be expressed as counts and percentages (%) and compared using either the chi-square test or Fisher’s exact test, as appropriate.

Continuous variables will be reported as median values (IQR), since normal distribution is not expected according to the Shapiro–Wilk test; between-group comparisons will be performed using the Mann–Whitney U test.

A repeated-measures analysis of variance (ANOVA) will be used to compare variables over time between groups. A Kaplan–Meier survival curve will be plotted for both groups and compared using the log-rank test. Missing data will be imputed using the mean linear interpolation method.

All statistical tests will be two-tailed, and a p-value < 0.05 will be considered statistically significant.

The analyses and figures will be performed using MedCalc software (Version 22.0.21, Ostend, Belgium) and GraphPad Prism (Version 10.2.3, Boston, Massachusetts, USA).

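### The Sample Size section gives two powers, two outcome types and an unexplained second infection rate, so the power behind 60 per group is not fixed

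*Protocol*

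**What the plan says.** The Sample Size section of the protocol has two short paragraphs.

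- The first sets the trial up as a comparison of two proportions, "with a 95% confidence level and 90% statistical power", and asks "whether the proportion of 59% in sample A differs from 29.5% in sample B, a total of 60 individuals per group will be required". It does not say which sample is placebo and which is trimethoprim–sulfamethoxazole.
- The second begins "This study aims to detect a clinically significant difference of 0.8", gives Zα/2 = 1.96, Zβ = 0.84 and an SD of 1.5, and ends by resting the calculations on the premise "that approximately 30% of patients with AKI will experience a subsequent infection". It names no variable or unit for the 0.8 and the 1.5, and no arm for the 30%.

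Three other places bear on this:

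- Operationalization of Variables, under "Dependent Variables (Primary Outcomes", lists thirteen outcomes. Twelve are yes/no and the last, adverse drug reactions, is nominal. None is continuous.
- Statistical Analysis says categorical variables will be "compared using either the chi-square test or" Fisher's exact test, with two-tailed tests at 0.05.
- Materials and Methods says "the subphenotype of patients at the highest risk of post-AKI infections will be selected".

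**The concern.** A sample-size statement should let a reader recover the outcome, the placebo rate, the target effect and the power. This one gives conflicting inputs.

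1. **Power.** 90% is stated, but Zβ = 0.84 corresponds to 80%. For 90% it would be 1.28.
2. **Outcome type.** Two proportions are followed by a mean difference with an SD. An SD of 1.5 cannot belong to a yes/no outcome, whose SD is at most 0.5.
3. **Infection rate.** 59% v 29.5% is followed by a statement that the calculations rest on about 30%, with no arm named.

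The first two are plain contradictions. The third is an ambiguity with large consequences. If 30% is the placebo rate, the trial could miss a true halving of infections about half the time, and a null result would say little. This is the protocol's only sizing statement, and an ethics committee or reader cannot tell from it which case applies.

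**Working it through.** **Inputs.** From Sample Size: 59%, 29.5%, 60 per group, 90% power, Zα/2 = 1.96, Zβ = 0.84, difference 0.8, SD 1.5, about 30%. From Statistical Analysis: two-sided 0.05, chi-square or Fisher's exact test. Equal allocation is implied by 60 per group.

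**Step 1: reproduce the 60.** With pooled variance, n per group = (zα/2 + zβ)² × 2p̄(1 − p̄) / d², where p̄ = (0.59 + 0.295)/2 = 0.4425 and d = 0.295.

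- 90% power: (1.96 + 1.2816)² × 2 × 0.4425 × 0.5575 / 0.295² = 59.6, so 60. The stated figure is reproduced.
- Other standard formulas at 90% give 55 (unpooled), 58 (pooled under the null, unpooled under the alternative) and 65 (continuity-corrected), so 60 is within the usual range.
- With the stated Zβ = 0.84: (1.96 + 0.84)² × 2 × 0.4425 × 0.5575 / 0.295² = 44.4, so 45. Zβ = 0.84 did not produce the 60.

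**Step 2: the means basis.** n per group = 2(zα/2 + zβ)² SD² / d².

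- Zβ = 0.84: 2 × 2.80² × 1.5² / 0.8² = 55.1, so 56.
- Zβ = 1.2816: 2 × 3.2416² × 1.5² / 0.8² = 73.9, so 74.
- With 60 per group the power is about 83%.

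Neither version gives 60, and 60 does not give 90% power on this basis.

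**Step 3: what the 30% could mean.** The powers below are for 60 per group, two-sided 5%. They were obtained by summing the binomial probabilities of every pair of event counts for which the test rejects.

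| Meaning of the 30% | Rates compared | Chi-square | Fisher |
|---|---|---|---|
| AKI in general; 59% is for the high-risk group selected | 59% v 29.5% | 92% | 88% |
| Rate in sample B | 59% v 30% | 91% | 87% |
| Average of both arms, with halving | 40% v 20% | 68% | 60% |
| Placebo rate, with halving | 30% v 15% | 51% | 42% |
| Placebo rate, cut to a third | 30% v 10% | 80% | 73% |

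The halving is carried over from 59% v 29.5%; the protocol does not state it for any other rate.

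**Step 4: where 60 per group is enough.**

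- With a 30% placebo rate, 90% power needs a treated rate of about 8% (7% with Fisher).
- A halving reaches 80% power only from a placebo rate of about 49% (53% with Fisher), and 90% only from about 57% (61%).
- For 30% v 15%, using the formula that pools under the null only, n = [1.96√(2p̄(1 − p̄)) + zβ√(p₁(1 − p₁) + p₂(1 − p₂))]² / d², with p̄ = 0.225 and d = 0.15. This gives 120.5, so 121 per group, at 80% power, and 160.8, so 161, at 90%.

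**The case against.** The strongest reply is that the basis of the 60 can be identified. The first paragraph gives two rates, a confidence level, a power and an n that agree, and nothing in the second paragraph leads to 60. On that view the second paragraph is stray text. The 30% may simply be sample B's 29.5% rounded, in which case the rates do not conflict. The 51% needs two assumptions that the protocol does not make: that 30% is the placebo rate, and that the halving carries over to it. The trial is also phase 2, with feasibility and safety aims.

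Much of this stands. The 60 is not a miscalculation, the rate problem is an ambiguity rather than a proven contradiction, and 51% is one end of a range.

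It does not remove the point. The sentence on 30% speaks of patients with AKI, not of treated patients, and says the calculations rest on it. The high-risk reading would explain 59% exceeding 30%, but then the calculation does not rest on 30%, and nothing in the protocol supports 59%. The one observed infection percentage, 42% in the Spanish cohort described under Background, covers a median of nine months starting three months after AKI, so it neither supports nor excludes 59% at 90 days. Whatever the 30% means, 90% against Zβ = 0.84 and proportions against means remain in conflict.

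**Conclusion.** The concern holds. The section is wrong as written in two respects (the power, and the type of outcome) and undefined in a third (the infection rate).

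The figure of 60 per group is correct for 59% v 29.5% at 90% power, two-sided 5%. Depending on what the 30% means, power for a halving runs from about 92% down to about 51% with the chi-square test, or from 88% to 42% with Fisher's exact test. The lower end assumes a 30% placebo rate and a halving to 15%.

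All these figures take the full 60 per group as analysed. If, as an assumption, 54 per group were analysed because patients are removed under Elimination Criteria, power for 59% v 29.5% would be 87% (83% with Fisher).

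This should be corrected before the trial relies on the stated power.

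**What to change.** Rewrite the Sample Size section on one binary basis:

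- Name the outcome as any infection within 90 days of discharge, if that is what is meant. Say which of A and B is placebo, and give one placebo rate with its justification, one treated rate and one power.
- Say what the 30% refers to, or delete it.
- Tie the sentence with 0.8, SD 1.5 and Zβ = 0.84 to a named secondary variable with its own stated power, or delete it.
- Keep 60 per group and say what it delivers. For example: *With 60 analysed per group and a two-sided 5% level, power is about 92% for 59% v 29.5%. If the placebo rate is 30%, it is about 51% for 30% v 15% and about 80% for 30% v 10% (chi-square; 88%, 42% and 73% with Fisher's exact test).*

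The cost is a change of text, with no extra patients or visits. The drawback is that the power claimed may become less favourable. If the team confirms a 30% placebo rate and a halving as the target, it must accept and report the lower power for this phase 2 trial; reaching 80% or 90% instead would take about 121 or 161 per group.

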#### Sampling Method

Potential participants for this study will be identified during routine hospital rounds for patients with acute kidney injury (AKI) and through concurrent review of medical records to confirm eligibility. If a patient is deemed eligible, the principal investigator will contact them to explain the study and provide a participant information and consent form.

After discussion with the patient and family members, the nephrology staff will obtain written informed consent prior to any study-related evaluations.

The intervention drug will be trimethoprim–sulfamethoxazole 800/160 mg, administered under double-blind conditions. Blinding will be achieved by ensuring that participants do not witness preparation of the study medication, and by assigning unblinded study personnel—who will not participate in outcome assessments—to handle preparation and administration.

The placebo will consist of magnesium tablets, administered at the same frequency—one tablet every 48 hours for three months.

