#### Required Resources

- The database will be compiled by the supervising resident physician and the

assigned medical intern.

- Material resources required include:
  - Computer equipment for data collection
  - Supply of trimethoprim–sulfamethoxazole 800/160 mg tablets, administered every 48 hours for three months per patient
  - The trimethoprim–sulfamethoxazole tablets will be funded by the research team itself.

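### The blinding method as written does not secure blinding of participants and treating clinicians, because it does not conceal the identity of two different tablets taken for three months after discharge

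*Protocol*

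**What the plan says.** Materials and Methods describes a "phase 2, randomized, prospective, double-blind, investigator-initiated, parallel-group, placebo-controlled clinical trial". The method of blinding is in Sampling Method and has two parts. The first concerns participants: "Blinding will be achieved by ensuring that participants do not witness preparation of the study medication". The second concerns staff: "assigning unblinded study personnel—who will not participate in outcome assessments—to handle preparation and administration".

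On the products, the same section states: "The placebo will consist of magnesium tablets, administered at the same frequency—one tablet every 48 hours for three months". Required Resources gives the active product as "800/160 mg tablets, administered every 48 hours for three months per patient", so both arms receive ready-made tablets on the same schedule.

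On the setting, Materials and Methods speaks of outpatient recruitment, and Observation Unit sets 90 days of monitoring after discharge. Elimination Criteria covers patients who stop the prophylactic antibiotic early or take a dose other than the one prescribed.

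Control Group Definition describes controls as discharged on standard post-AKI care without antibiotic prophylaxis and does not mention the placebo. Required Resources lists the active tablets and their funding but no placebo.

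**The concern.** Keeping preparation out of the patient's sight works for a product that staff make up and give on site, such as an infusion. It does little for a finished tablet, because what could reveal the allocation is the tablet itself, its imprint, taste or label, and the patient meets these at every dose. The comparator is a different product, and the protocol does not say that the two look alike or are packed alike. A treating clinician who is shown the tablets or the container is in the same position.

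This matters because of how the outcomes arise. Operationalization of Variables lists gastrointestinal, upper and lower respiratory, urinary and soft-tissue infections among the primary outcomes, along with adverse drug reactions. Under Data Collection and Observation Techniques, data are extracted from the hospital's electronic record. A mild infection enters that record only if the patient seeks care and a clinician records a diagnosis. If either of them knows or guesses the arm, care seeking, recording and use of other antibiotics can differ between arms, and a difference in recorded infections can appear without any drug effect. Blinding that is lost during follow-up cannot be restored in the analysis.

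**Working it through.** **Step 1: what each stated measure protects.**

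| Party | Measure stated | Does it conceal the tablet's identity? |
|---|---|---|
| Participant | Does not see preparation | No. The tablet is ready-made and is seen when taken |
| Treating clinician | None named | No |
| Outcome assessor | Unblinded staff are kept out of assessment | Helps, unless the patient or the record reveals the arm |

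No section mentions matched appearance, over-encapsulation, coded containers or labelling.

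**Step 2: exposure.** 90 days × 24 hours / 48 hours = 45 tablets per patient.

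**Step 3: who handles the tablets.** The protocol does not say outright that patients take the tablets at home. The inference rests on three places: outpatient recruitment (Materials and Methods), patients who stop or who take a different dose from the one prescribed (Elimination Criteria), and a three-month tablet supply per patient (Required Resources). Against it, Sampling Method gives administration to unblinded staff. Staff administration of some 45 doses per outpatient over 90 days is hard to reconcile with the rest of the text. The passages need reconciling whichever is meant.

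**Step 4: what biased recording would do (illustration).** The protocol has no figure for this, so there is nothing of its own to reproduce.

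Inputs: n = 60 per arm and two-sided α = 0.05 (Sample Size; Statistical Analysis); true infection risk p₂ = 0.30 in both arms (an assumption, close to the approximate 30% that Sample Size gives for subsequent infection); recorded control-arm risk p₁ = 0.30 + d, with d = 0.05, 0.10 or 0.15 (assumed; nothing in the protocol supports a value).

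Formulas, with p̄ = (p₁ + p₂)/2:

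- s₀ = √[2p̄(1 − p̄)/n]
- s₁ = √[p₁(1 − p₁)/n + p₂(1 − p₂)/n]
- P(reject) = Φ[(d − 1.96 s₀)/s₁] + Φ[(−d − 1.96 s₀)/s₁]

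For d = 0.10: s₀ = √(2 × 0.35 × 0.65/60) = 0.0871 and s₁ = √(0.24/60 + 0.21/60) = 0.0866. The first argument is (0.10 − 0.1707)/0.0866 = −0.816, which gives 0.207. The second term is about 0.001. The total is 0.208.

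| Spurious rise in control arm | Normal approximation | Chi-square, exact enumeration | Fisher's exact, enumeration |
|---|---|---|---|
| 0 | 5.0% | 5.2% | 3.1% |
| 5 points | 9.0% | 9.2% | 6.0% |
| 10 points | 20.8% | 21.0% | 15.5% |
| 15 points | 39.5% | 39.8% | 32.4% |

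The two enumeration columns sum the binomial probabilities of all tables with 60 per arm that the test rejects at 0.05. The chi-square is uncorrected. Statistical Analysis allows either test.

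**The case against.** **Silence is not failure.** A reader might infer that the tablets look different and that the double-blind claim is therefore false. The protocol does not say that. The placebo may be a matched product, and preparation by unblinded staff could include repackaging or encapsulation. This stands, and it limits the point to blinding that is not secured by the method as written.

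**Assessors are covered.** The second half of the blinding sentence keeps unblinded staff out of outcome assessment. This also stands. The gap concerns participants and treating clinicians.

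**Each patient sees one product.** In a parallel-group trial there is no side-by-side comparison, so unblinding needs a recognisable imprint, label or taste, or patients comparing notes. The protocol describes none of these. This lowers the likelihood of unblinding. It does not make hidden preparation a safeguard.

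**Record extraction and hard outcomes.** Data come from the electronic record, and death, long-term renal replacement therapy, hyperkalaemia and eGFR decline are less open to reporting bias. That is fair for those outcomes. For milder infections, extraction leaves care seeking and diagnostic recording untouched.

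**The resource list and control definition.** A reader might take these to mean that no placebo is planned or that controls are untreated. Sampling Method and the treatment variable both provide for a placebo, so that reading fails. Silence in a short resource list is weak evidence. What remains is an inconsistency to tidy.

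**The bias is hypothetical.** It is. The table shows what bias of a given size would do, not that it is likely.

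**Conclusion.** The point holds as an inexpensive improvement that should be made. The protocol does not leave the blinding method open. It names two measures, and neither conceals the identity of finished tablets of two different products taken for three months. Followed as written, it leaves participants and treating clinicians open to unblinding, while many of the infection outcomes depend on what those people do. The documents do not show that the tablets are distinguishable, that blinding is impossible, or that assessors are unprotected.

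Two things are inferred or assumed. Self-administration is inferred and conflicts with the wording on staff administration. The inflation of the false-positive rate to about 9%, 21% or 40% (about 6%, 15% or 32% with Fisher's exact test) assumes a 30% true risk in both arms and a spurious rise of 5, 10 or 15 points in one direction.

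**What to change.** In Sampling Method, replace the blinding sentence with a statement to this effect: active and placebo units are indistinguishable (matched tablets or the same opaque over-capsule). They are supplied in identical numbered containers, packed to the randomisation list by the unblinded personnel already planned, who take no part in care or outcome assessment. Participants, treating clinicians and outcome assessors are blinded.

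In the same section, state whether patients take the tablets themselves after discharge, and reconcile this with the wording on staff administration and with Elimination Criteria. Add the placebo supply to Required Resources, and align Control Group Definition with the placebo control.

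The cost is a protocol revision and a one-off supply or encapsulation expense for 120 patients at about 45 units each, which is 120 × 45 = 5,400 units. The protocol gives no prices, so calling this modest is a judgement. It needs to be settled before dispensing. No change to the sample size or the analysis is required.

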#### Secondary Objectives:

To evaluate the risk of rehospitalization, infection-related rehospitalization, septic shock, major adverse kidney events (MAKE) at 90 days, incidence of hyperkalemia, and new episodes of acute kidney injury. Adverse events (AEs) will be coded using the Medical Dictionary for Regulatory Activities (MedDRA) and classified as mild, moderate, or severe. AEs of special interest include skin rash, erythema, nausea, vomiting, headache, and tachycardia.

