#### Control Group Definition

The control group will include patients who, during hospitalization at the Old Civil Hospital of Guadalajara “Fray Antonio Alcalde”, were identified by the Nephrology Service as having severe acute kidney injury that had resolved or was in the process of recovery. These patients will have been discharged with standard post-AKI management and care, without the addition of antibiotic prophylaxis.

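### The comparator named as placebo is a magnesium tablet of unstated composition, which can mask gastrointestinal reactions to the study drug and, less directly, blur gastrointestinal infection

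*Protocol*

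**What the plan says.** All references are to the Protocol.

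- Materials and Methods calls the study a "phase 2, randomized, prospective, double-blind, investigator-initiated, parallel-group, placebo-controlled clinical trial".
- Operationalization of Variables defines treatment as a "categorical variable with two levels: active treatment or placebo".
- Sampling Method fixes the comparator: "The placebo will consist of magnesium tablets, administered at the same frequency", that is, "one tablet every 48 hours for three months". No salt, strength or matching of appearance is given, and no reason for choosing magnesium. Participant blinding is said to rest on patients not seeing the medication prepared and on unblinded staff who handle it but do not assess outcomes.
- Control Group Definition describes controls as patients whose severe AKI has resolved or is resolving, discharged on standard care "without the addition of antibiotic prophylaxis". It does not mention the tablet.
- Secondary Objectives states: "AEs of special interest include skin rash, erythema, nausea, vomiting, headache, and tachycardia".
- The outcome list in Operationalization of Variables includes "Development of gastrointestinal infections" as a yes/no item and adverse drug reactions, both under the primary outcomes. Neither has a diagnostic criterion.
- Required Resources lists trimethoprim–sulfamethoxazole tablets and no placebo product.

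**The concern.** A placebo arm is meant to show what happens without any pharmacological effect from the tablet. A magnesium tablet does not guarantee that, and the Protocol offers nothing to show that this one is neutral. The choice of comparator is made in the Protocol itself and is not something a statistical analysis plan would settle.

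Two comparisons are exposed, to different degrees.

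- **Tolerability, directly.** Nausea, vomiting and adverse drug reactions are counted in both arms. Any such event caused by the control tablet raises the reference rate and narrows the observed excess on the study drug. Safety is one of the three stated phase 2 aims, so this matters on its own. Blinding does not remove it, because the events would be real.
- **Efficacy, indirectly.** Magnesium does not cause infection. Without a criterion for gastrointestinal infection, however, tablet-related symptoms could be recorded as one.

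**Working it through.** **1. The sections side by side.** Materials and Methods and Operationalization of Variables say placebo. Sampling Method says magnesium. No section says the tablet is inert, gives its composition or justifies it. The label and the product are not reconciled anywhere.

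**2. Exposure.** 90 days at one tablet every 2 days is 90 / 2 = 45 tablets per patient, and 45 × 60 = 2,700 for the control arm.

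**3. The plan's own sample size, as a check on the method.** Sample Size gives 59% v 29.5%, 90% power, two-sided 0.05 and 60 per group. With the pooled-variance formula and mean proportion 0.4425:

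n = [1.96 × √(2 × 0.4425 × 0.5575) + 1.2816 × √(0.59 × 0.41 + 0.295 × 0.705)]² / 0.295² = (1.377 + 0.860)² / 0.0870 ≈ 57.5, so 58.

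This is within 2 patients of 60, and power at 60 per group is 0.912. The point does not rest on this figure.

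**4. Formula for the illustrations.** For true recorded rates p1 and p2 with n = 60 per arm, d = p1 − p2 and mean rate p̄:

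s0 = √(2p̄(1 − p̄)/60), s1 = √((p1(1 − p1) + p2(1 − p2))/60)

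P(significant in favour of a higher p1) = Φ((d − 1.96·s0)/s1). The opposite tail uses −d in place of d.

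**5. Masking of tolerability (all rates assumed).** Suppose nausea occurs in 20% on the drug and would occur in 5% on an inert tablet.

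| Control tablet adds | Comparison | s0 | s1 | Power to see the excess |
|---|---|---|---|---|
| 0 points | 20% v 5% | 0.0604 | 0.0588 | 0.70 |
| 2 points | 20% v 7% | 0.0624 | 0.0613 | 0.55 |
| 5 points | 20% v 10% | 0.0652 | 0.0645 | 0.33 |

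**6. Misclassification as infection (all rates assumed).** Suppose the drug has no effect and true infection risk is 30% in both arms. That is close to the roughly 30% in the second paragraph of Sample Size. A share m of *uninfected* controls is wrongly counted as infected, and nobody on the drug is. The recorded control rate is then 0.30 + 0.70m.

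| m | Recorded control rate | Favouring drug | Favouring control | Two-sided false-positive rate |
|---|---|---|---|---|
| 0 | 30.0% | 2.5% | 2.5% | 5.0% |
| 2% | 31.4% | 3.6% | 1.7% | 5.3% |
| 5% | 33.5% | 6.1% | 0.9% | 6.9% |
| 10% | 37.0% | 12.5% | 0.3% | 12.8% |

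Last row in full: p̄ = 0.335, s0 = 0.0862, s1 = 0.0859. (0.07 − 0.1689)/0.0859 = −1.15, giving 0.125. (−0.07 − 0.1689)/0.0859 = −2.78, giving 0.003.

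**7. If the drug arm is misclassified too.** At half the control share, the three non-zero rows become 31.4% v 30.7%, 33.5% v 31.75% and 37.0% v 33.5%. The false-positive rates are then about 5.1, 5.5 and 6.8%. At equal shares the rate returns to 5%. At a higher share on the drug, the bias runs against the drug.

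**8. Choice of test.** The Protocol allows chi-square or Fisher's exact test. For 37% v 30%, exact enumeration gives about 13% for the uncorrected chi-square test and about 9% for Fisher's.

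**The case against.** The strongest reply is that one tablet of unknown content every 48 hours may have no material gastrointestinal effect, and the documents cannot show otherwise. That stands, and is why the point says *can* cause symptoms. It does not answer the gap: the Protocol uses the word placebo without stating what the tablet contains or why it is neutral.

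A reader might infer more than the text supports, in four ways.

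- **That Control Group Definition contradicts Sampling Method.** It does not. It excludes antibiotic prophylaxis and never says standard care *only*; magnesium is not an antibiotic. The section omits the tablet and should mention it.
- **That gastrointestinal effects are recorded only in the control arm.** The Protocol lists nausea and vomiting as events to watch for on the study drug. If symptoms are scored as infection, this can happen in both arms, so the net efficacy bias may be nil or reversed.
- **That no difference could be attributed to the antibiotic.** The outcome list also includes urinary, respiratory and soft tissue infections, infection-related rehospitalization and septic shock. No route from magnesium to these is apparent.
- **That the error rate could reach 33% or 21%.** These figures come from adding 10 points to every control patient: 20% v 10% for gastrointestinal infection, 40% v 30% for any infection. Both assume no misclassification on the drug, and the second counts already infected controls again. If the drug arm gains half as many events, 20% v 15% gives about 11%. Counting only uninfected controls, 37% v 30% gives about 13%.

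It is also fair to say that nothing in the Protocol states that infections are counted on symptoms alone, and detailed endpoint rules may sit elsewhere. The efficacy route is therefore a possibility. The tolerability route does not depend on it.

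**Conclusion.** The point holds in a limited form. The Protocol names a substance that is not pharmacologically inert as its placebo, without composition, matching or justification. The firmest consequence is for tolerability: any gastrointestinal events from the control tablet reduce the apparent excess on the study drug. On the assumed nausea rates, 5 added points cut power from 0.70 to 0.33.

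For efficacy the consequence is conditional. It needs symptoms to be recorded as infection, and more often in controls than on the drug. With 30% true risk in both arms and up to 10% of uninfected controls misclassified, the two-sided false-positive rate is at most about 13%. It is lower under Fisher's test or with partial misclassification on the drug. The misclassification and nausea rates are assumptions; none is in the Protocol. That magnesium can cause gastrointestinal symptoms is general pharmacology, and how often it would here depends on the unstated salt and strength. The change is worth making before recruitment but does not by itself invalidate the trial.

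**What to change.** - **Sampling Method:** replace the magnesium tablet with a tablet containing no active ingredient, matched in appearance to the study tablet. Matching also supports blinding, because not seeing the preparation is weak protection when outpatients take tablets for three months.
- **Control Group Definition:** state that controls receive this placebo in addition to standard post-AKI care.
- **Required Resources:** add the placebo to the list of supplies.

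Cost: about 2,700 inert matched tablets (45 × 60) in place of the magnesium tablets, plus the wording. The Protocol gives no unit price and says that the team pays for the active tablets itself, so the supply needs a source and a budget line. No extra patients or visits are needed, and the study drug regimen is untouched.
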